Trichotillomania	10044629

HLGT Sleep Disorders and Disturbances

Notes: Medical concept of sleep disorders. All preferred terms from (1) HLGT 'Sleep Disorders and Disturbances', 'Psychiatric disorders' SOC plus (2)HLGT 'Sleep disturbances (incl subtypes)', 'Nervous system' SOC. Numerous duplicated preferred terms e.g. middle insomnia

PT	PT Code
Behavioural insomnia of childhood	10072072
Hyposomnia	10067530
Initial insomnia	10022035
Insomnia	10022437
Middle insomnia	10027590
Terminal insomnia	10068932
Breathing-related sleep disorder	10006344
Dyssomnia	10061827
Hypersomnia	10020765
Periodic limb movement disorder	10064600
Pickwickian syndrome	10035004
Poor quality sleep	10062519
Sleep apnoea syndrome	10040979
Somnolence	10041349
Somnolence neonatal	10041350
Stupor	10042264
Upper airway resistance syndrome	10063968
Cataplexy	10007737
Hypnagogic hallucination	10020927
Hypnopompic hallucination	10020928
Narcolepsy	10028713
Sleep attacks	10040981
Sleep paralysis	10041002
Abnormal dreams	10000125
Abnormal sleep-related event	10061613
Confusional arousal	10067494
Exploding head syndrome	10080684
Loss of dreaming	10065085
Nightmare	10029412
Parasomnia	10061910
Rapid eye movement sleep behaviour disorder	10077299
Rapid eye movements sleep abnormal	10037841
Sleep inertia	10067493
Sleep sex	10067492
Sleep talking	10041009
Sleep terror	10041010
Sleep-related eating disorder	10067315
Somnambulism	10041347
Hypersomnia related to another mental condition	10020767
Hypersomnia-bulimia syndrome	10053712
Insomnia related to another mental condition	10022443
Sleep disorder	10040984
Sleep disorder due to a general medical condition	10063910
Sleep disorder due to general medical condition, hypersomnia type	10040985
Sleep disorder due to general medical condition, insomnia type	10040986
Sleep disorder due to general medical condition, mixed type	10040987
Sleep disorder due to general medical condition, parasomnia type	10040988

PT	PT Code
Sopor	10058709
Advanced sleep phase	10001423
Circadian rhythm sleep disorder	10009191
Delayed sleep phase	10012209
Irregular sleep phase	10022995
Irregular sleep wake rhythm disorder	10080301
Non-24-hour sleep-wake disorder	10078086
Shift work disorder	10078088

HLGT Sleep disturbances (incl subtypes)	
PT	PT Code
Abnormal dreams	10000125
Abnormal sleep-related event	10061613
Confusional arousal	10067494
Loss of dreaming	10065085
Sleep inertia	10067493
Sleep paralysis	10041002
Sleep sex	10067492
Sleep talking	10041009
Sleep terror	10041010
Sleep-related eating disorder	10067315
Somnambulism	10041347
Behavioural insomnia of childhood	10072072
Hyposomnia	10067530
Initial insomnia	10022035
Insomnia	10022437
Middle insomnia	10027590
Terminal insomnia	10068932
Advanced sleep phase	10001423
Circadian rhythm sleep disorder	10009191
Delayed sleep phase	10012209
Irregular sleep phase	10022995
Irregular sleep wake rhythm disorder	10080301
Non-24-hour sleep-wake disorder	10078086
Shift work disorder	10078088
Cataplexy	10007737
Hypersomnia	10020765
Narcolepsy	10028713
Central-alveolar hypoventilation	10007982
Sleep apnoea syndrome	10040979
Breathing-related sleep disorder	10006344
Dysomnia	10061827
Fatal familial insomnia	10072077
Microsleep	10076954
Periodic limb movement disorder	10064600
Pickwickian syndrome	10035004
Poor quality sleep	10062519
Rapid eye movement sleep behaviour disorder	10077299
Rapid eye movements sleep abnormal	10037841
Sleep deficit	10080881
Sudden onset of sleep	10050014

PT	PT Code
Upper airway resistance syndrome	10063968

Convulsions (SMQ)		20000079	Notes: Medical concept of seizures. Only narrow terms from SMQ 'Convulsions' selected plus selected PTs of possible seizure events from HLT 'Disturbances in consciousness NEC' under SOC 'Nervous systems disorders' and HLT 'Confusion and disorientation' under SOC 'Psychiatric disorders' .
PT	PT Code		
2-Hydroxyglutaric aciduria	10078971		
Acquired epileptic aphasia	10052075		
Acute encephalitis with refractory, repetitive partial seizures	10076948		
Alcoholic seizure	10056347		
Aspartate-glutamate-transporter deficiency	10079140		
Atonic seizures	10003628		
Atypical benign partial epilepsy	10056699		
Automatism epileptic	10003831		
Autonomic seizure	10049612		
Baltic myoclonic epilepsy	10054895		
Benign familial neonatal convulsions	10067866		
Benign rolandic epilepsy	10070530		
Biotinidase deficiency	10071434		
Change in seizure presentation	10075606		
Clonic convulsion	10053398		
Convulsion in childhood	10052391		
Convulsion neonatal	10010911		
Convulsions local	10010920		
Convulsive threshold lowered	10010927		
CSWS syndrome	10078827		
Deja vu	10012177		
Double cortex syndrome	10073490		
Dreamy state	10013634		
Drug withdrawal convulsions	10013752		
Early infantile epileptic encephalopathy with burst-suppression	10071545		
Eclampsia	10014129		
Epilepsy	10015037		
Epilepsy surgery	10079824		
Epileptic aura	10015049		
Epileptic psychosis	10059232		
Febrile convulsion	10016284		
Febrile infection-related epilepsy syndrome	10079438		
Focal dyscognitive seizures	10079424		
Frontal lobe epilepsy	10049424		
Generalised non-convulsive epilepsy	10018090		
Generalised tonic-clonic seizure	10018100		
Glucose transporter type 1 deficiency syndrome	10078727		
Gray matter heterotopia	10080533		
Hemimegalencephaly	10078100		
Hyperglycaemic seizure	10071394		

PT	PT Code
Hypocalcaemic seizure	10072456
Hypoglycaemic seizure	10048803
Hyponatraemic seizure	10073183
Idiopathic generalised epilepsy	10071081
Infantile spasms	10021750
Juvenile myoclonic epilepsy	10071082
Lafora's myoclonic epilepsy	10054030
Lennox-Gastaut syndrome	10048816
Migraine-triggered seizure	10076676
Molybdenum cofactor deficiency	10069687
Multiple subpial transection	10079825
Myoclonic epilepsy	10054859
Myoclonic epilepsy and ragged-red fibres	10069825
Partial seizures	10061334
Partial seizures with secondary generalisation	10056209
Petit mal epilepsy	10034759
Polymicrogyria	10073489
Post stroke epilepsy	10076982
Post stroke seizure	10076981
Postictal headache	10052470
Postictal paralysis	10052469
Postictal psychosis	10070669
Postictal state	10048727
Post-traumatic epilepsy	10036312
Schizencephaly	10073487
Seizure	10039906
Seizure anoxic	10039907
Seizure cluster	10071350
Seizure like phenomena	10071048
Severe myoclonic epilepsy of infancy	10073677
Simple partial seizures	10040703
Status epilepticus	10041962
Sudden unexplained death in epilepsy	10063894
Temporal lobe epilepsy	10043209
Tonic clonic movements	10051171
Tonic convulsion	10043994
Tonic posturing	10075125
Topectomy	10073488
Tuberous sclerosis complex	10080584
Uncinate fits	10045476

PTs (Selective)	
Confusional state	10010305

PT	PT Code
Loss of consciousness	10024855
Syncope	10042772
Sopor	10058709
Stupor	10042264
Altered state of consciousness	10050093
Depressed level of consciousness	10012373
Consciousness fluctuating	10050093

Acute renal failure (SMQ)		20000003	Notes: Medical concept of worsening renal function/renal failure in the context of impact on creatinine. Only narrow terms from SMQ 'Acute renal failure' plus all PTs from HLT 'Renal failure and impairment', under SOC 'Renal and urinary disorders'. Numerous duplicated preferred terms e.g. renal failure
PT	PT Code		
Acute kidney injury	10069339		
Acute phosphate nephropathy	10069688		
Anuria	10002847		
Azotaemia	10003885		
Continuous haemodiafiltration	10066338		
Dialysis	10061105		
Foetal renal impairment	10078987		
Haemodialysis	10018875		
Haemofiltration	10053090		
Hyponatriuria	10077515		
Neonatal anuria	10049778		
Nephropathy toxic	10029155		
Oliguria	10030302		
Peritoneal dialysis	10034660		
Prerenal failure	10072370		
Renal failure	10038435		
Renal failure neonatal	10038447		
Renal impairment	10062237		
Renal impairment neonatal	10049776		

Renal Failure and Impairment HLT	
PT	PT Code
Acute Kidney injury	10069339
Anuria	10002847
Atypical haemolytic uraemic syndrome	10079840
Cardiorenal syndrome	10068230
Chronic kidney disease	10064848
Crush syndrome	10050702
Diabetic end stage renal disease	10012660
End stage renal disease	10077512
Foetal renal impairment	10078987
Haemolytic uraemic syndrome	10018932
Hepatorenal failure	10019845
Hepatorenal syndrome	10019846

PT	PT Code
Nail-patella syndrome	10063431
Neonatal anuria	10049778
Oliguria	10030302
Pancreatorenal syndrome	10056277
Postoperative renal failure	10056675
Postrenal failure	10059345
Prerenal failure	10072370
Propofol infusion syndrome	10063181
Renal failure	10038435
Renal failure neonatal	10038447
Renal impairment	10062237
Renal impairment neonatal	10049776
Renal injury	10061481
Scleroderma renal crisis	10062553
Traumatic anuria	10044501

Tubulointerstitial diseases (SMQ)	20000221	Notes: Medical concept of Proximal Renal Tubule Dysfunction. Only narrow terms from SMQ 'Tubulointerstitial diseases'.
PT	PT Code	
Acidosis hyperchloraemic	10000489	
Acquired aminoaciduria	10073515	
Acute phosphate nephropathy	10069688	
Aminoaciduria	10001939	
Beta-N-acetyl-D-glucosaminidase increased	10004511	
Crystal nephropathy	10071503	
Eosinophils urine present	10058363	
Fanconi syndrome acquired	10052607	
Hyperphosphaturia	10051232	
Isosthenuria	10023077	
Nephritis allergic	10029120	
Nephrogenic diabetes insipidus	10029147	
Nephropathy toxic	10029155	
Renal glycosuria	10038457	
Renal papillary necrosis	10038491	
Renal tubular acidosis	10038535	
Renal tubular atrophy	10038536	
Renal tubular disorder	10038537	
Renal tubular dysfunction	10050335	
Tubulointerstitial nephritis	10048302	
Tubulointerstitial nephritis and uveitis syndrome	10069034	
Urine phosphorus increased	10055030	
Urine retinol binding protein increased	10061432	

Proteinuria (SMQ)		20000220	Notes: Medical concept of Proteinuria. Only narrow terms from narrow SMQ 'Proteinuria' included.
PT	PT Code		
Albumin globulin ratio increased	10001567		
Albumin urine present	10001582		
Albuminuria	10001580		
Bence Jones protein urine present	10053112		
Bence Jones proteinuria	10004231		

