3.3.1. Risk Assessment

Potential Risk of Clinical Significance	Summary of Data/Rationale for Risk	Mitigation Strategy

Drug Induced Liver Injury (DILIs)
	
A small proportion of participants in the CAB program to date (total exposure approximately 1644 to 01 April 2017) have developed transaminitis (elevated liver transaminases characterized by predominant Alanine aminotransferase [ALT] elevation). In most participants, transient transaminitis was explained by acute hepatitis C infection (majority) and other systemic infections. In a small number of participants, there was not an alternative explanation, suggesting a mild form of DILI without hepatic dysfunction which resolved upon withdrawal of treatment with CAB. Of the four participants with suspected of DILI identified in Phase 2 HIV treatment studies, all were receiving oral CAB.
	
 • Exclusion criteria as described in Section 6.2 will prohibit participants with significant liver impairment based on screening liver chemistry including transaminases (ALT and aspartate aminotransferase [AST]) as well as on prior medical history. Participants with a history of chronic liver disease with ongoing inflammation and/or fibrosis will be excluded. • A 4-week oral lead- in Phase is being implemented in this study, where all participants will receive oral CAB prior to the administration of IM CAB to assess individual tolerance to systemic drug. • Liver transaminases (ALT and AST) will be closely monitored throughout this study (refer to SoA Table 1) and the liver chemistry stopping criteria will be adopted as described in Section 8.1.1 of this protocol. Participants will be withdrawn from CAB treatment where no compelling alternative cause is identified and DILI is suspected. • Participants who develop ALT ≥ 3 times the upper limit of normal (ULN) while on study must consult with Medical Monitor prior to initiation or continuation of CAB LA.

Potential Risk of Clinical Significance	Summary of Data/Rationale for Risk	Mitigation Strategy

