For participants with Grade ≥ 3 diarrhea that is unresponsive to the recommended dose of the anti-motility agents and for which an alternative etiology (e.g., infectious diarrhea) is not established, the treatment with the anti-motility agent and IP must be interrupted until resolution of diarrhea to Grade ≤ 2 or Baseline, after which IP and background ART may be resumed after discussion and agreement with the Medical Monitor. If Grade ≥ 3 diarrhea recurs within 28 days upon the resumption of IP, the IP should be permanently discontinued and the participant withdrawn from the study.

If loperamide is used for treatment of diarrhea, local prescribing information should be followed with respect to dose and frequency of administration. Loperamide dosing should not exceed local prescribing information.

Hypertriglyceridemia/ Hypercholesterolemia

Samples for lipid measurements must be obtained in a fasted state according to the SoA table (Section 2). Participants who experience asymptomatic triglyceride or cholesterol elevations may continue to receive IP. Clinical management of participants with hypertriglyceridemia/hypercholesterolemia should not be based upon non-fasting samples (obtained in the fed state). A confirmatory fasting triglyceride and/or cholesterol level should be obtained prior to the institution of medical therapy for hyperlipidemia. Isolated Grade 3 and Grade 4 lipid abnormalities do not require withdrawal of IP.

Please see the Recommendations of the Adult AIDS Clinical Trial Group Cardiovascular Disease Focus Group [Dube, 2003] for full discussion of management of hyperlipidemia in the context of HIV therapy.

Decline in Renal Function

Participants who experience an increase in serum creatinine from Baseline of 45 micromoles/liter ($\mu\text{Mol/L}$) (or 0.5 milligrams/deciliter [mg/dL]) should return for a confirmatory assessment within 2 to 4 weeks. A urinalysis and urine albumin/creatinine and urine total protein/albumin ratios should also be done at this confirmatory visit. If the creatinine increase is confirmed, the investigator should contact the study medical monitor to discuss additional follow-up and medical management.

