In the absence of the above signs or symptoms, participants with Grade 2 allergic reaction may continue the study drug at the discretion of the Investigator. The participant should be advised to contact the Investigator immediately if there is any worsening of the allergic reaction and/or if any systemic signs or symptoms worsen. If the allergic reaction is considered to be most likely due to concomitant illness or non-study medication, standard management, including discontinuation of the likely causative agent, should be undertaken. If no other causative factor is found after clinical evaluation, the participant may be treated symptomatically until the rash resolves. Antihistamines, topical corticosteroids or antipruritic agents may be prescribed. The participant should remain on the study to be followed for safety and PK as outlined in Section 2.

Grade 3 allergic reaction (Generalized urticaria or angioedema):

Participants will permanently discontinue the study medication and be withdrawn from the trial. Participants will be treated as clinically appropriate. Participants should be followed up until resolution of the adverse event and standard management should be undertaken.

Grade 4 allergic reaction (Anaphylaxis):

Participants will permanently discontinue the study medication and be withdrawn from the trial. Participants will be treated as clinically appropriate. Participants should be followed up until resolution of the adverse event and standard management should be undertaken.

Revised ACTG Toxicity Grade	Definitions	Investigator Action
Grade 1	Pruritus without rash	May continue therapy
Grade 2	Localized urticaria	May continue therapy
Grade 3	Generalized urticaria Angioedema	Discontinue Therapy
Grade 4	Anaphylaxis	Discontinue Therapy

12.9. Appendix 9: HIV Testing Algorithm and Management of HIV Infection in Study Participants

- HIV testing at Day 1 and the subsequent visits will use POC HIV testing kits in accordance with local standard operating procedures. Additional testing is required for participants who have a reactive or positive HIV test after enrolment. Stored plasma from the visit previous to the positive test should be tested for HIV using the 4th generation HIV test to best estimate time of infection. HIV acquisition must be confirmed by either western blot, HIV ½ Multispot or the Geenius HIV Confirmation ½ Assay, and HIV RNA ([Branson](#), 2014).

[figure not shown]
Reference:

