2. SUMMARY OF KEY PROTOCOL INFORMATION

2.1. Changes to the Protocol Defined Statistical Analysis Plan

The current adverse events of special interest (AESIs) included in the protocol are seizures and seizure like events, diarrhea, hypertriglyceridemia/hypercholesterolemia, decline in renal function, proximal renal tubule dysfunctions and proteinuria.

We are modifying the study AESIs to align them with the rest of the Cabotegravir programme, now that the AESIs related to CAB have now been fully developed.

The RAP AESIs will differ from the AESIs defined in the protocol. AESIs of hepatotoxicity, hypersensitivity reactions, injection site reactions, impact on creatinine, and neuropsychiatric events have been added to the list of AESIs for the RAP.

The events of diarrhea, hypertriglyceridemia/hypercholesterolemia, have been removed for the list of AESIs in the RAP.

Seizures and seizure like events, Decline in renal function, proximal renal tubule dysfunctions, proteinuria, which were defined in the protocol, will be kept as the AESIs for the study.

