10.6.3. Safety**Adverse Events****Adverse Events of Special Interest**

- Seizures and seizure like events
- Decline in Renal Function
- Proximal Renal Tubule Dysfunctions
- Proteinuria
- Hepatotoxicity
- Hypersensitivity Reactions
- Injection Site Reactions
- Impact on Creatinine
- Neuropsychiatric Events

The adverse events of special interest that were used for data summaries are provided in Section [10.16](#)

Laboratory Parameters

- HIV-1 RNA: For summaries and analyses which use HIV-1 RNA level as a continuous measure, the logarithm to base 10 of the value will be used.
- If a laboratory value which is expected to have a numeric value for summary purposes, has a non-detectable level reported in the database, where the numeric value is missing, but typically a character value starting with '<x' or '>x' (or indicated as less than x or greater than x in the comment field) is present, the number of significant digits in the observed values will be used to determine how much to add or subtract in order to impute the corresponding numeric value.
 - Example 1: 2 Significant Digits = '< x' becomes $x - 0.01$
 - Example 2: 1 Significant Digit = '> x' becomes $x + 0.1$
 - Example 3: 0 Significant Digits = '< x' becomes $x - 1$

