10.16. Appendix 16: Adverse Events of Special Interest Used for Data Summaries

AESI Item	Product of Interest	PT Selection*
Hepatic Safety Profile: Assessment of risk of hepatotoxicity	CAB +RPV	Sub- SMQ** x2
Hypersensitivity reactions (HSR)	CAB	SMQ (modified) plus selected PTs from HLGT
Severe cutaneous adverse reactions (SCAR)	RPV	SMQ plus selected PTs from HLTs
Prolongation of the corrected QT interval of the ECG in supratherapeutic doses	RPV	SMQ plus selected PT from HLT
Neuropsychiatric Events 
 •Suicidal ideation/behaviour •Depression •Bipolar disorder •Psychosis •Mood disorders •Anxiety •Sleep disorders 	CAB +RPV	SMQ , Sub- SMQ or HLGT
Injection Site Reactions (ISR)	CAB +RPV	Use CRF terms for ISRs
Seizures and seizure-like events	CAB	SMQ plus selected PTs from HLTs
Impact on Creatinine/Decline in Renal function	CAB+RPV	SMQ plus selected PTs from HLT
Safety in Pregnancy	CAB	Use AE terms co-reported in pregnancy exposures to CAB
Proteinuria	CAB+RPV	SMQ
Proximal Renal Tubule Dysfunctions	CAB+RPV	SMQ

* All PTs, SMQs, HLT, HLGTs from MedDRA V21
** All SMQs use narrow terms unless otherwise specified

Hepatic failure, fibrosis and cirrhosis and other liver damage-related conditions (SMQ)

2000013

*Notes: Medical concept of hepatic failure and hepatitis. Sub-SMQs (1) 'Hepatic failure, fibrosis and cirrhosis and other liver damage-related conditions' **and** (2) 'Hepatitis, non-infectious', both of parent SMQ 'Hepatic Disorders'; only narrow terms selected from sub-SMQs. Some preferred terms e.g PT 'hepatitis fulminant' are duplicated.*

PT	PT Code
Acquired hepatocerebral degeneration	10080860
Acute hepatic failure	10000804
Acute on chronic liver failure	10077305
Acute yellow liver atrophy	10070815
Ascites	10003445
Asterixis	10003547
Bacterascites	10068547
Biliary cirrhosis	10004659
Biliary fibrosis	10004664
Cholestatic liver injury	10067969
Chronic hepatic failure	10057573
Coma hepatic	10010075
Cryptogenic cirrhosis	10063075
Diabetic hepatopathy	10071265
Drug-induced liver injury	10072268
Duodenal varices	10051010
Gallbladder varices	10072319
Gastric variceal injection	10076237
Gastric variceal ligation	10076238
Gastric varices	10051012
Gastric varices haemorrhage	10057572
Hepatectomy	10061997
Hepatic atrophy	10019637
Hepatic calcification	10065274
Hepatic cirrhosis	10019641
Hepatic encephalopathy	10019660
Hepatic encephalopathy prophylaxis	10066599
Hepatic failure	10019663
Hepatic fibrosis	10019668

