Drug reaction with eosinophilia and systemic symptoms syndrome (SMQ) -		
Notes: Medical concept of hypersensitivity reactions/DRESS. Only narrow terms selected from Category A of SMQ 'Drug reaction with eosinophilia and systemic symptoms syndrome'. Algorithmic approach for this SMQ not used due to complexity in applying and poor specificity of remaining categories. Category A selected as PTs because more specific for concept (only narrow terms) and a pre-requisite for any combination in algorithmic search. Overlap of some preferred terms with SMQ 'Severe Cutaneous Adverse Reactions'. Plus additional preferred terms selected from HGLT 'Allergic conditions' under SOC 'Immune system disorders'

	20000225	
PT	PT Code	
Drug reaction with eosinophilia and systemic symptoms	10073508	
Pseudolymphoma	10037127	

PTs (Selective)	
Drug hypersensitivity	10013700
Hypersensitivity	10020751
Type IV Hypersensitivity reaction	10053613
Eosinophilia	10014950
Eye swelling	10015967
Eyelid oedema	10015993
Lip swelling	10024570
Angioedema	10002424
Circumoral oedema	10052250
Face oedema	10016029
Idiopathic angioedema	10073257
Lip oedema	10024558
Mouth swelling	10075203
Oedema mouth	10030110
Periorbital oedema	10034545
Swelling face	10042682

Severe cutaneous adverse reactions (SMQ)		20000020	Notes: Medical concept of severe cutaneous adverse reactions. Only narrow terms from SMQ 'Severe cutaneous adverse reactions' selected. Plus several additional preferred terms [only G3 and higher] selected from HLTs 'Rashes, eruptions and exanthems NEC', 'Pruritus NEC', 'Pustular conditions', 'Dermatitis ascribed to specific agent' all under SOC 'Skin and subcutaneous tissue disorders'
---	--	-----------------	--

PT	PT Code
Acute generalised exanthematous pustulosis	10048799
Cutaneous vasculitis	10011686
Dermatitis bullous	10012441
Dermatitis exfoliative	10012455
Dermatitis exfoliative generalised	10012456
Drug reaction with eosinophilia and systemic symptoms	10073508
Epidermal necrosis	10059284
Erythema multiforme	10015218
Exfoliative rash	10064579
Oculomucocutaneous syndrome	10030081
Skin necrosis	10040893
Stevens-Johnson syndrome	10042033
Toxic epidermal necrolysis	10044223
Toxic skin eruption	10057970

PTs (Selective)G3 and higher	
Eyelid rash	10074620
Genital rash	10018175
Mucocutaneous rash	10056671
Nodular rash	10075807
Perineal rash	10075364
Rash	10037844
Rash erythematous	10037855
Rash generalised	10037858
Rash macular	10037867
Rash maculo-papular	10037868

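### Three special-interest categories in SAP Appendix 16 have no term for creatinine rise, urticaria/anaphylaxis or transaminase rise, so their counts in Table 2.17 and Listing 20 can be incomplete

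*SAP*

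**What the plan says.** SAP section 2.1 brings the special-interest events into line with the cabotegravir programme: "AESIs of hepatotoxicity, hypersensitivity reactions, injection site reactions, impact on creatinine, and neuropsychiatric events have been added". It also retains four protocol items, decline in renal function among them. SAP section 10.6.3 names nine items and then states: "The adverse events of special interest that were used for data summaries are provided in Section" 10.16, which is Appendix 16. Appendix 16 therefore decides what is counted in Table 2.17 and Listing 20. Injection site reactions are taken from CRF terms. The three categories at issue are set by MedDRA preferred-term lists, with no laboratory or grade criterion beside them:

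- Hypersensitivity: "Medical concept of hypersensitivity reactions/DRESS. Only narrow terms selected from Category A of SMQ 'Drug reaction with eosinophilia and systemic symptoms syndrome", plus a selected set of further terms.
- Hepatotoxicity: "Medical concept of hepatic failure and hepatitis", using narrow terms from two sub-SMQs.
- Impact on creatinine and decline in renal function, combined in one row: "Medical concept of worsening renal function/renal failure in the context of impact on creatinine", using narrow acute renal failure terms plus the renal failure and impairment HLT.

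The protocol describes the corresponding events as follows.

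- Liver (section 3.3.1): "transaminitis (elevated liver transaminases characterized by predominant Alanine aminotransferase [ALT] elevation", with a few unexplained cases read as mild drug-induced liver injury.
- Allergy (Appendix 8): localized urticaria is Grade 2, generalized urticaria or angioedema is Grade 3, and the top grade begins "Grade 4 allergic reaction (Anaphylaxis".
- Kidney (Appendix 4, decline in renal function): "Participants who experience an increase in serum creatinine from Baseline of 45 micromoles/liter" return for confirmation, as do those whose eGFR falls by more than half.

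**The concern.** A special-interest table is read one category at a time, and a zero is taken to mean that the named risk was not seen. If the term list does not hold the event by which the protocol recognises that risk, the zero may only mean that the investigator recorded a finding and not a diagnosis. Safety of the injection is a primary objective, and about 40 men are to be injected. One or two events settle whether a category reads zero.

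**Working it through.** The SAP gives no figure to reproduce. The check is a reading of each list against the protocol, with a search for the relevant word stems.

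**Completeness of the lists.** The overview table in Appendix 16 gives the parts of each list: two sub-SMQs for liver, a modified SMQ plus selected terms for hypersensitivity, and an SMQ plus HLT terms for kidney. All of these parts are present. The proteinuria list is cut short in the available text and was not assessed.

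**Search results.**

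| Category | Terms in list | Stems searched | Matches | Listed terms that would catch a diagnosis |
|---|---|---|---|---|
| Creatinine / renal decline | 46 rows, 36 distinct | creatinine, glomerular, filtration rate, clearance | 0 | Renal impairment, Renal failure, Acute kidney injury |
| Hypersensitivity | 18 | urticaria, anaphylaxis | 0 | Hypersensitivity, Drug hypersensitivity, Angioedema |
| Hepatotoxicity | 102 rows, 99 distinct | transaminase, aminotransferase, enzyme, function test | 0 | Drug-induced liver injury, Hepatotoxicity, Liver injury |

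The severe cutaneous list (34 terms) has no urticaria or anaphylaxis term, so it does not fill the gap. The other RAP text in the same file has no Appendix 16 and does not fill it either.

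**Allergic reactions.** Appendix 8 uses four presentations for Grades 2 to 4: localized urticaria, generalized urticaria, angioedema and anaphylaxis. The list names one of the four, angioedema.

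**Whether a bare finding can be an AE.** Protocol Appendix 4 counts an abnormal laboratory result as an AE when the investigator judges it clinically significant. It asks for the diagnosis in preference to signs, but only where possible. An asymptomatic ALT or creatinine rise can therefore properly be recorded as the finding. Urticaria and anaphylaxis are natural terms for an investigator to write down.

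**Where the events still appear.**

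- All AEs: Tables 2.3 to 2.5 and the AE listings, subject to the grade cut-off of Table 2.5.
- Creatinine: the grading table puts 1.3 times baseline at Grade 2. With baseline B, (B + 45)/B ≥ 1.3 holds when B ≤ 45/0.3 = 150 µmol/L. A 45 µmol/L rise from any such baseline enters Table 2.16. An eGFR fall of 50% or more is Grade 4.
- ALT: a value of at least 3 times ULN triggers the liver-event form (Table 2.26, Listing 36). Table 2.27 covers hepatobiliary laboratory abnormalities.
- Allergy: Appendix 8 requires permanent discontinuation at Grades 3 and 4, which leads to Table 2.8 and Listing 19.

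**How likely an event is at all.** The documents give no rates for these events, so the rates here are assumptions. With n = 40, P(at least one) = 1 − (1 − p)^40:

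- p = 2%: 1 − 0.98^40 = 55%
- p = 5%: 1 − 0.95^40 = 87%
- p = 10%: 1 − 0.90^40 = 98.5%

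These are chances that an event occurs. The chance that it is left out of its category also depends on how it is coded, which cannot be estimated from the documents.

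**The case against.** The best defence is that the lists are deliberate and diagnosis-based. SAP section 2.1 gives programme alignment as the reason, the hepatic and renal notes specify narrow terms, and the hypersensitivity note explains why the full DRESS algorithm was not used. Protocol section 3.3.1 describes hypersensitivity to the drug class as rash with constitutional signs and sometimes organ dysfunction, which is close to a DRESS picture. Appendix 8 is a toxicity-management section and does not define special-interest events. Investigators are asked for diagnoses, the main diagnoses are listed, and laboratory rises have displays of their own.

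Most of this stands. It makes the omission conditional on coding and limits the damage. It does not justify the gap:

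- The reasons given concern the DRESS algorithm. They do not explain a list that holds lip oedema and eye swelling but not anaphylaxis.
- The appendix is not consistently diagnosis-only. Eosinophilia, a QT prolongation finding and raised urine phosphorus all appear in its lists.
- For the kidney, the SAP keeps the protocol's own item while its list has no term for the changes by which the protocol identifies it.

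A reader might infer that the special-interest output as a whole would be almost empty, or that these events would vanish from the report. Neither follows. Injection site reactions are a special-interest item and the protocol expects them in most participants, so the table and listing should be well filled.

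**Conclusion.** The point holds at the level of category counts. In Table 2.17 and Listing 20, the counts for impact on creatinine/decline in renal function, hypersensitivity and hepatotoxicity will be incomplete whenever an event is coded to the finding itself. The renal part is the strongest, because the SAP expressly retains that protocol item. The hypersensitivity gap is partial, and so is the hepatic one, since the leading liver-injury diagnoses are listed. This rests on the lists being applied as printed and on some events being recorded as findings.

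Two further steps might be inferred, and the documents support neither:

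- Adding bilirubin to hepatotoxicity. The protocol expects bilirubin rises in carriers of reduced-function UGT1A1 variants and accepts isolated, mainly indirect elevation at entry. Bilirubin terms would mix that effect into a liver-injury count.
- Deleting the rilpivirine rows as irrelevant. The severe cutaneous row carries Stevens-Johnson syndrome, toxic epidermal necrolysis and Grade 3 or higher rash, which the protocol's rash grades also describe.

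**What to change.** Keep the programme lists in Appendix 16 and add one study-specific row to each of the three categories, with exact names checked against the MedDRA version in use:

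- Impact on creatinine/decline in renal function: blood creatinine increased; GFR decreased; creatinine clearance decreased.
- Hypersensitivity: urticaria; anaphylactic reaction; anaphylactic shock.
- Hepatotoxicity: ALT increased; AST increased; transaminases increased.

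Show the programme-defined and study-defined counts side by side in Table 2.17, and flag both definitions in Listing 20. Leave the severe cutaneous list in place. Reconcile the nine items in SAP section 10.6.3 with the eleven rows of Appendix 16, which merge two of the nine and add severe cutaneous reactions, QT prolongation and pregnancy.

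The cost is a term-list edit, a few table rows and a listing flag. The drawback is a study-defined count that differs from the programme's, which is why both should be shown.
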